#### **9.4.3.2 Treatment emergent AEs**

The following events are considered treatment emergent:

Adverse events with an onset date on or after first dose of IP and within 30 days after last dose of IP or up to the day prior to start of subsequent therapy, whichever comes first.

Worsening of pre-existing events on or after first dose of IP and within 30 days after last dose of IP or up to the day prior to start of subsequent therapy, whichever comes first.

Exposure-adjusted treatment emergent AEs will also be presented.

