3.3.2.3 On-Treatment Safety Period

For the purposes of summarising safety data assessed at visits, in addition to baseline data, only on-treatment data are included in the summary tables. On-treatment data will be defined as data from the first dose of study intervention until the last dose of study intervention + 30 days.

The On-Treatment Safety Period will be further subset into the On-treatment Safety Randomised Period and On-selumetinib Safety Period.

If the On-Treatment Safety Period of a patient is still ongoing at the time of the analysis, their on-treatment safety period will be truncated at the DCO date, and any measurement/event with a start date after the DCO date will be presented at a later DCO.

On-treatment Safety Randomised Period.

The on-treatment safety randomised period for patients receiving selumetinib in the randomised period will be defined as the date from the first dose of study intervention until the first date when the selumetinib kit(s) are dispensed as recorded in the drug accountability form at or after the Cycle 12 Day 28 visit date or 30 days after study intervention discontinuation or up to one day prior to start of subsequent therapy, whichever occurs first.

The on-treatment safety randomised period for patients receiving only placebo in the randomised period will be defined as the date from the first dose of study intervention until the date when the first selumetinib kit(s) are dispensed as recorded in the drug accountability form (crossover date) or 30 days after placebo discontinuation or up to one day prior to the start of subsequent therapy, whichever occurs first.

If the on-treatment randomised period of a patient is still ongoing at the time of the analysis, their on-treatment randomised period will be truncated at the DCO date, and any measurement/event with a start date after the DCO date will be presented at a later DCO.

On-Selumetinib Safety Period

The on-selumetinib safety period will be defined as the date from the first dose of selumetinib until 30 days after the last dose of selumetinib or up to one day prior to the start of subsequent therapy, whichever occurs first.

The baseline definition for patients receiving placebo in the randomised period and then crossing over to selumetinib either on Cycle 13 Day 1 or earlier in the case of progression will differ for the on-treatment safety randomised period and the on-selumetinib period as described in Section [3.3.1](#).

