3.3.2.4 Treatment-emergent Periods

The analysis of treatment-emergent adverse events (TEAEs) and concomitant medication will be performed separately for TEAEs occurring/concomitant medication taken during the safety randomised period and TEAEs occurring/concomitant medication taken during the on-selumetinib period. While the analysis of TEAEs in the safety randomised period will be comparative of the two treatment groups, TEAEs presented for the on-selumetinib period will be not comparative due to the different exposure periods. To note, the two safety analysis periods are not mutually exclusive.

TEAEs and Concomitant Medication during the Safety Randomised Period

For patients receiving any selumetinib in the safety randomised period, an adverse event (AE) or a concomitant medication is considered treatment emergent during the safety randomised period if the start date/time of the event or worsening date/time (only for AEs) occurs between the date of first dose of study intervention (Cycle 1 Day 1) and last dose of Cycle 12 or date of study intervention discontinuation (end of treatment [EOT]) + 30 days or DCO date, whichever comes first.

For patients receiving placebo in the safety randomised period, an AE or a concomitant medication is considered treatment emergent during the safety randomised period if the start date/time of the event, or worsening date/time of an AE occurs between the date of first dose of placebo (Cycle 1 Day 1) and the crossover date or date of early placebo discontinuation + 30 days or DCO, whichever comes first.

A worsening is defined as having any on-treatment severity during the safety randomised period worse than the baseline severity. The reported severity of an AE that is treatment emergent during the safety randomised period is given by the maximum Common

Terminology Criteria for Adverse Events (CTCAE) grade recorded any time on-treatment during the safety randomised period. The reported outcome of an AE will be the last outcome corresponding to the maximum CTCAE grade recorded on-treatment in the safety randomised period. Seriousness and causality during the randomised period will also be reported as the worst value recorded in the safety randomised period.

TEAEs and Concomitant Medication during the On-Selumetinib Period

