An AE or a concomitant medication is considered treatment-emergent during the on-selumetinib period if the start date/time of the event, or worsening date/time of a AE occurs between the first dose of selumetinib (which will be Cycle 1 Day 1 for patients receiving selumetinib in the safety randomised period and the date of the crossover for patients receiving placebo in the safety randomised period) until 30 days after the last dose of selumetinib or up to DCO, whichever comes first.

A worsening is defined as having any on-treatment severity during the on-selumetinib period worse than the severity of the safety randomised period. Worsening in the on-selumetinib period will be assessed by comparing to the last-recorded value in the safety randomised period.

For AEs of placebo patients starting during the safety randomised period and worsening during the On-Selumetinib period, the stop date of the event during the safety randomised period will be one day prior to the date of the first worsening after crossing over, while the start date of the event during the on-selumetinib period will be equal to the date of first worsening after crossing over.

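### The SAP's treatment-emergent AE windows omit the protocol's subsequent-therapy limit and, in the randomised period, count 30 days from discontinuation instead of last dose

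*SAP*

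**What the plan says.** Protocol 9.4.3.2 applies one end rule to new events and to worsening of existing ones. Both must fall "within 30 days after last dose of IP or up to the day prior to start of subsequent therapy, whichever comes first".

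SAP 3.3.2.4 sets three windows:

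- Randomised period, any selumetinib: ends at "last dose of Cycle 12 or date of study intervention discontinuation (end of treatment [EOT]) + 30 days or DCO date, whichever comes first".
- Randomised period, placebo: ends at "the crossover date or date of early placebo discontinuation + 30 days or DCO, whichever comes first".
- On-selumetinib period: runs "until 30 days after the last dose of selumetinib or up to DCO, whichever comes first".

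SAP 3.3.2.3 defines the on-treatment safety periods for data assessed at visits. Its general definition is "data from the first dose of study intervention until the last dose of study intervention + 30 days". It then narrows this. For selumetinib in the randomised period the limits include "30 days after study intervention discontinuation or up to one day prior to start of subsequent therapy, whichever occurs first", and the placebo sentence is built in the same way. The on-selumetinib period runs "until 30 days after the last dose of selumetinib or up to one day prior to the start of subsequent therapy, whichever occurs first".

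SAP 4.6.2.2 ties the AE summary tables to Section 3.3.2.4. SAP Section 2, which lists changes from the protocol's planned analyses, mentions neither difference. The SAP's amendment history records edits to these definitions but no decision to remove the limit.

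**The concern.** There are two separate departures. First, none of the three windows in 3.3.2.4 stops when a participant starts another NF1-PN therapy. An AE that begins after that therapy can be tabulated as emergent on study treatment, which the protocol rule prevents.

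Second, the randomised-period windows start the 30 days at discontinuation, while the protocol and the on-selumetinib window start them at last dose. When a participant discontinues during a dose interruption, the two dates differ and the randomised-period window reaches further past the last dose.

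This also breaks the relation between the two sets of tables. For someone randomised to selumetinib, the on-selumetinib period should contain the randomised period. With different anchors, a late AE can be treatment-emergent in the shorter period and not in the longer one. The randomised-period tables are the ones the SAP describes as comparative between arms.

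**Working it through.** The plan states no figure on this point, so the check is a comparison of rules followed by day counts.

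**Step 1. Rules side by side**

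| Place | 30 days counted from | Stops before subsequent therapy? |
|---|---|---|
| Protocol 9.4.3.2 | last dose | yes |
| SAP 3.3.2.3, randomised period, selumetinib | discontinuation | yes |
| SAP 3.3.2.3, randomised period, placebo | placebo discontinuation | yes |
| SAP 3.3.2.3, on-selumetinib | last dose | yes |
| SAP 3.3.2.4, randomised period, selumetinib | discontinuation (EOT) | no |
| SAP 3.3.2.4, randomised period, placebo | early placebo discontinuation | no |
| SAP 3.3.2.4, on-selumetinib | last dose | no |
| SAP 4.6.2.2, time at risk for those without the event | last dose | no |

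The missing limit is confined to 3.3.2.4 and the rate denominator. The discontinuation anchor is in the randomised-period rules of both 3.3.2.3 and 3.3.2.4.

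**Step 2. Can discontinuation fall after last dose?** Yes. SAP 4.6.1.1 provides for permanent discontinuation during an interruption and then uses the last administration for exposure. The end-of-treatment footnote to protocol Table 1 allows for an EoT visit more than 30 days after last dose. The documents do not say how often either happens.

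**Step 3. Size of the anchor effect.** Let L be the days from last dose to discontinuation/EOT. L is an assumption, shown over a range.

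- Protocol window ends at day 30 after last dose.
- SAP randomised-period window ends at day L + 30, so the nominal overrun is L.
- AE collection ends when follow-up is complete (protocol 8.3.1), and the follow-up visit is at last dose + 30 (+7) days (protocol 4.1). Collection therefore stops by day 37, or at the EoT visit if that is later: day max(37, L).
- Effective overrun = min(L + 30, max(37, L)) − 30.

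| L | SAP window ends, day | Nominal overrun, days | Effective overrun, days |
|---|---|---|---|
| 0 | 30 | 0 | 0 |
| 7 | 37 | 7 | 7 |
| 14 | 44 | 14 | 7 |
| 28 | 58 | 28 | 7 |
| 31 | 61 | 31 | 7 |
| 45 | 75 | 45 | 15 |

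This applies only to participants who stop before the end of Cycle 12. For the others the window closes at the last Cycle 12 dose or at crossover.

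**Step 4. Size of the missing limit.** Let S be the day after last dose on which subsequent therapy starts (also assumed). The protocol window ends at day min(30, S − 1) and the on-selumetinib window at day 30. Extra days = 30 − min(30, S − 1).

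| S | Protocol ends, day | Extra days in SAP |
|---|---|---|
| 1 | 0 | 30 |
| 7 | 6 | 24 |
| 14 | 13 | 17 |
| 28 | 27 | 3 |

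**Step 5. Nesting.** Take L = 28 in a participant randomised to selumetinib who stops before the end of Cycle 12. The randomised-period window ends on day 58 and the on-selumetinib window on day 30. An AE on day 34, if collected, is treatment-emergent in the first and not in the second.

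**The case against.** The best defence is that 3.3.2.4 inherits the limit. It opens by speaking of events in the safety randomised period and the on-selumetinib period, and SAP 4.1.8.2 says those periods are defined in 3.3.2.3, where the limit appears. But 3.3.2.4 then gives its own complete earliest-of rule for each window, and 4.6.2.2 sends the AE tables there. A programmer following the text would not apply the limit.

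Other arguments reduce the size, and they stand. Other systemic PN treatment is not allowed during the study (protocol Appendix J 2), and participants who discontinue normally stay for the 30-day follow-up. Early subsequent therapy should therefore be uncommon, though protocol 7.1 lists starting it as a reason for discontinuation. Safety is summarised descriptively, no test depends on these windows, and every AE is listed. The exposure-adjusted rate has no internal mismatch today, because its numerator window and denominator both use last dose + 30 days without the limit.

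A reader might infer more from protocol 6.6, which requires discontinuation when a related AE has not resolved to Grade 1 or less within 4 weeks of onset, subject to event-specific guidance. On that reading the window for toxicity discontinuations usually runs 28 days too long. With an assumed 5 to 15 such discontinuations among 73, that gives 28 × 5 = 140 to 28 × 15 = 420 extra person-days, mostly on selumetinib. The documents do not support this. The 4 weeks run from AE onset and not from the last dose, the EoT visit is due as soon as possible after the decision, and no discontinuation frequency or split by arm is given. Collection also caps the overrun at 7 days for L = 28, so the same assumption gives 7 × 5 = 35 to 7 × 15 = 105 person-days.

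**Conclusion.** Both departures are real on the text, and neither is declared. SAP 3.3.2.4 departs from protocol 9.4.3.2 on the subsequent-therapy limit in all three windows and on the anchor in the two randomised-period windows. On the limit it also disagrees with SAP 3.3.2.3.

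The effect is likely small. The off-drug overrun is about 7 days per affected participant unless the EoT visit falls after day 37. The missing limit can add up to 30 days of post-therapy AEs per affected participant in the on-selumetinib window. These sizes rest on assumed values of L and S and on AE collection stopping at follow-up or at a later EoT visit. The number of participants affected cannot be derived from the documents.

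A reader might also infer that the rule inflates the selumetinib arm systematically. The discontinuation anchor applies to both arms, and nothing in the documents shows that the gaps differ between them. The correction is worth making because an undeclared change to a protocol-defined safety rule leaves two conflicting definitions in the SAP. It does not threaten the trial's main conclusions.

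**What to change.** 1. In SAP 3.3.2.4, end every TEAE window at the earliest of: last dose + 30 days; the day before subsequent NF1-PN therapy; DCO; and, for the randomised period only, last dose of Cycle 12 or crossover.
2. In SAP 3.3.2.3, change the randomised-period definitions to count 30 days from last dose. Copying 3.3.2.3 as it stands into 3.3.2.4 would restore the limit but keep the wrong anchor.
3. In SAP 4.6.2.2, add the subsequent-therapy limit to the exposure-adjusted denominator, so that events and time at risk stop on the same day.
4. If the departure is intended, list it in SAP Section 2 with a reason.

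The cost is SAP wording and one end-date derivation used in three places. The start of subsequent therapy is already needed for the primary estimand. A few late AEs would leave the tables and remain in the listings.

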3.3.1 Baseline Definition and Change From Baseline

There will be two baseline definitions for the study.

In general, for efficacy (excluding the Extended Selumetinib FAS) and PRO endpoints (see also Section 3.3.8 for further information on derivation of baseline for certain PRO endpoints), the last observed measurement prior to randomisation will be considered the baseline measurement. However, if an evaluable assessment is only available after randomisation but before the first dose of randomised treatment, then this assessment will be used as the baseline. For the Extended Selumetinib FAS (defined in Section 3.2.5), baseline will be defined as the last non-missing value obtained prior to the first dose of selumetinib.

For safety endpoints (excluding the on-selumetinib safety analysis set), the last observation before the first dose of study intervention will be considered the baseline measurement unless otherwise specified.

If two or more measurements are recorded on the same day with no time (or on the same day with the same time/timepoint) then the average will be used as the baseline. If these measurements occur on the day where a patient crosses over from placebo to selumetinib, the pre-crossover value will be used as the baseline. If there are multiple pre-crossover measurements, then the average of the pre-crossover measurements will be used as the baseline. For non-numeric laboratory tests (i.e., some of the urinalysis parameters) where taking an average is not possible, the best value would be taken as the baseline as this is the most conservative.

For the on-selumetinib safety analysis set (defined in Section 3.2.8), baseline will be defined as the last non-missing value obtained prior to the first dose of selumetinib.

In all summaries, change from baseline variables will be calculated as the post-treatment value minus the value at baseline. The percentage change from baseline is calculated as $(\text{post-baseline value} - \text{baseline value}) / (\text{baseline value}) * 100$.

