4.6.2.2 Presentation

Summary tables of the number and percentage of patients with AEs by SOC and PT will be produced for below categories. An overall summary table will include the number and percentage of patients in each category.

- All AEs
- AEs possibly related to study intervention
- AEs of CTCAE grade 3 or higher
- AEs with CTCAE grade 3 or higher, possibly related to study intervention
- AEs with an outcome of death
- AEs with an outcome of death possibly related to study intervention
- All SAEs
- SAEs possibly related to study intervention
- AEs leading to discontinuation of study intervention
- AEs leading to discontinuation of study intervention, possibly related to study intervention
- AEs leading to dose interruption of study intervention
- AEs leading to dose reduction of study intervention
- AESIs
- OAEs

Patients with more than one event in any category are only counted once in each category (i.e., multiple events are not accounted for).

Additionally, the most common AEs, which are those AEs that occur in at least 10% of patients overall, are summarised by PT and by decreasing frequency. This cut-off may be modified after review of the data. When applying a cut-off (eg, 10%), the raw percentage should be compared to the cut-off, and no rounding should be applied first (ie, an AE with frequency 9.9% does not appear if the cut-off is 10%).

A separate table will present non-serious AEs occurring in more than 5% of patients in any treatment group.

CTCAE grades and summaries of the number and percentage of patients will be provided by SOC, PT, and maximum reported CTCAE grade. A summary table of AESIs by maximum reported CTCAE grade will be produced.

Each summary table above will be presented for TEAEs during the randomised period and for TEAEs during the on-selumetinib period as defined in Section 3.3.2.4.

For the summaries of on-selumetinib TEAEs, in addition to number and number and percentage of patients [n(%)], exposure-adjusted incidence rates (per 100 person-years) will be reported. These are derived as:

$$\frac{\text{Number of participants with AE}}{\text{Total on - selumetinib person - years}} \times 100$$

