where the total on-selumetinib person-years is given by the sum of all the individual durations of exposure until experiencing the first occurrence of the AE across all patients in the on-selumetinib period. For those patients experiencing the AE, duration of exposure will be calculated as (first occurrence AE start date – first selumetinib dose date +1)/365.25. For those patients not experiencing the AE, it will be equal to (min(last selumetinib dose date +30 days, date of study discontinuation, DCO) – first selumetinib dose date +1)/365.25.

The number of patients in the placebo treatment group might differ for the randomised period and on-selumetinib period. Patients who were randomised and treated with placebo but discontinued prior to them being able to start on selumetinib will not be counted in the on-selumetinib period but will be counted in the randomised period.

All reported AEs will be listed for the safety analysis set. The key listings which will be produced are the following:

- AEs with an outcome of death – key subject information
- SAEs – key subject information
- AEs leading to discontinuation of study intervention – key subject information
- AEs leading to dose modification (dose interruption and/or dose reduction of study intervention) – key subject information
- AESIs – key subject information
- All AEs – listing of key information

Key listings will be split by treatment group using subheadings.

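### For participants on selumetinib from Cycle 1 Day 1, the on-selumetinib AE tables judge worsening of a pre-dose event against an on-drug grade

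*SAP*

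**What the plan says.** SAP 3.3.2.4 defines two treatment-emergent periods. For participants who receive selumetinib from the start, both begin at Cycle 1 Day 1, and the section acknowledges the overlap: "To note, the two safety analysis periods are not mutually exclusive".

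The reference grade for worsening differs between the periods. In the safety randomised period: "A worsening is defined as having any on-treatment severity during the safety randomised period worse than the baseline severity". In the on-selumetinib period: "Worsening in the on-selumetinib period will be assessed by comparing to the last-recorded value in the safety randomised period". The second sentence names no arm. The only arm-specific text there is the next paragraph, which splits start and stop dates. It opens "For AEs of placebo patients starting during the safety randomised period and worsening during the On-Selumetinib period" and moves the on-selumetinib start date to the first worsening after crossover.

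SAP 3.3.1 already gives a pre-drug reference for the on-selumetinib safety set: "baseline will be defined as the last non-missing value obtained prior to the first dose of selumetinib". Protocol 9.4.3.2 likewise treats worsening of a pre-existing event from first dose onward as treatment emergent.

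SAP 4.6.2.2 produces every AE summary table for both periods. The on-selumetinib version adds exposure-adjusted incidence rates. The person-time rule for affected participants begins "For those patients experiencing the AE, duration of exposure will be calculated as (first occurrence AE start date"; it then subtracts the first selumetinib dose date, adds 1 and divides by 365.25.

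**The concern.** A worsening rule needs a reference grade from before the treatment under study. For a placebo participant who crosses over, the final randomised-period grade is such a reference. For a participant on selumetinib from Day 1 it is not: the grade was recorded on drug, up to 12 cycles into the on-selumetinib period itself. The randomised-period and on-selumetinib tables can therefore disagree about the same event in the same weeks, and in either direction.

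There is a linked gap over dates. The start-date reset covers only placebo participants' events that begin in the randomised period. An event that began in screening, in either arm, and qualifies by worsening is not covered. Its recorded onset then enters the person-time formula and precedes the first selumetinib dose.

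At stake are the counts and rates in the on-selumetinib AE tables for events that qualify only by worsening.

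**Working it through.** **Which events are exposed.** AEs are collected from consent (Protocol 8.3.1) and changes in grade are recorded (Protocol 8.3.2). An event that starts on or after the first selumetinib dose qualifies by its start date, whatever the worsening rule says. The comparator therefore matters only for selumetinib-arm events (about 73 participants) with onset between consent and first dose, a screening window of up to 28 days, that later change grade.

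**Comparator.** Let b be the pre-dose grade, g1 and g2 an early and the last randomised-period grade, and g3 a later grade. The event is truly worse if max(g1, g2, g3) > b. The rule in SAP 3.3.2.4 can be read in three ways:

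- A: any grade in the on-selumetinib period exceeds g2.
- B: g3 exceeds g2.
- C: g3 exceeds max(g1, g2).

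| Path (b, g1, g2, g3) | Truly worse? | A | B | C |
|---|---|---|---|---|
| (1, 3, 3, 3) | yes, 3 > 1 | not flagged (3 vs 3) | not flagged (3 vs 3) | not flagged (3 vs 3) |
| (3, 1, 1, 2) | no, maximum after dosing is 2 | flagged (2 > 1) | flagged (2 > 1) | flagged (2 > 1) |
| (1, 3, 3, 4) | yes, 4 > 1 | flagged (4 > 3) | flagged (4 > 3) | flagged (4 > 3) |

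The first path counts in the randomised-period table (3 > 1) but not in the on-selumetinib table that contains those weeks. The second is the reverse error. The third shows that the rule does not always fail.

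Enumerating all paths with b from 1 to 3 and each g from 1 to 4 gives 3 × 64 = 192 paths, of which 156 are truly worse and 36 are not. Missed and falsely flagged paths are 70 and 16 under A, 95 and 11 under B, and 120 and 6 under C. These are counts of logical possibilities. They show that every reading errs in both directions; they are not expected frequencies.

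**Start date.** The formula in SAP 4.6.2.2 is AE start date − first selumetinib dose date + 1, with no lower bound. Set the first study dose at index 0.

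- Selumetinib arm, onset 1, 14 or 28 days before first dose: −1 + 1 = 0; −14 + 1 = −13; −28 + 1 = −27 days.
- Placebo arm, assuming crossover on Day 337 (12 × 28 + 1, index 336), onset 14 days before the first placebo dose: −14 − 336 + 1 = −349 days, and −349 / 365.25 = −0.96 person-years.
- Same arm, onset 28 days before: −28 − 336 + 1 = −363 days, or −0.99 person-years.

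Each such participant adds one to the numerator of that AE row and subtracts from its denominator (or adds nothing, when the result is 0), so the rate is inflated.

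**The case against.** The strongest reply is that the comparator sentence was evidently written for crossovers. The date-splitting paragraph after it concerns placebo participants, SAP 4.6.2.1 gives the example of an event that starts in the randomised period and worsens on selumetinib, and SAP 3.3.1 supplies the right baseline. That is probably the intent, but the text does not restrict the sentence, and 3.3.1 cannot override a different comparator named explicitly.

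A second reply is to read the rule chronologically, judging each worsening against the grade recorded just before it. This would rescue (1, 3, 3, 3). It departs from the stated comparator, though, and still wrongly flags (3, 1, 1, 2), because 2 exceeds the preceding 1.

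Third, nothing says in words that a screening-onset event keeps its original start date, and the prose around the exposure formula speaks of time to first occurrence within the on-selumetinib period. A careful programmer might substitute the worsening date. That is fair: the negative times are conditional on applying the printed formula to the recorded start date. But that is what the formula asks for, and the reset is not extended to these events.

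The case for low materiality stands. Grade 3 events before dosing should be uncommon given the entry criteria. A placebo example also needs a screening event still open after 12 cycles that then worsens. The SAP itself says "TEAEs presented for the on-selumetinib period will be not comparative due to the different exposure periods".

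**Conclusion.** The rule is wrong as written for participants on selumetinib from Day 1. It can miss true worsening and count false worsening, and it conflicts with the SAP's own on-selumetinib baseline and its randomised-period rule. The start-date provision is incomplete in both arms and, taken literally, allows non-positive person-time.

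The reach is small. Only events with onset before first dose are involved. How many there will be, and the net direction of the comparator error, cannot be derived from the documents. Because "Patients with more than one event in any category are only counted once in each category", a missed event removes a participant from a row only if nothing else qualifies there. The comparative randomised-period tables, the AE listings and all efficacy tests are unaffected. The change is worth making but optional.

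The conclusion assumes that SAP 3.3.2.4 and 4.6.2.2 are programmed as printed. The placebo-arm figures also assume crossover on Day 337.

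**What to change.** In the on-selumetinib part of SAP 3.3.2.4:

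1. Define worsening for everyone against the last severity recorded before the first selumetinib dose. That is the grade before Cycle 1 Day 1 in the selumetinib arm and the last pre-crossover grade in placebo participants who cross over.
2. For any event in either arm that began before the first selumetinib dose and qualifies only by worsening, including placebo participants' events with screening onset, set the on-selumetinib start date to the first worsening after that dose.

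The first change aligns the rule with SAP 3.3.1 and Protocol 9.4.3.2 and keeps the crossover handling. The second removes zero and negative times from the exposure formula. The cost is one paragraph and the matching derivation; the grades and dates needed are already collected.
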